4.2. Treatment Arms and Duration

Subjects will be randomized in a 2:2:1 ratio to receive:

- 15 mg FBE IV DNX BID +75 mg OSV BID;
- 50 mg FBE IV DNX BID + 75 mg OSV BID; or
- IV DNX placebo BID + 75 mg OSV BID

Treatment duration will be up to 5 days ([Figure 2](#)). The investigator may elect to continue open-label oseltamivir treatment. If a subject is discharged from the hospital in less than 5 days, treatment with IV DNX will discontinue, irrespective of whether the investigator elects to continue oral OSV treatment at discharge. Follow up will continue until Day 45 for all subjects.

Figure 2 Study Schematic

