7.1. Time and Events Table

Table 3 Time and Events Table: Assessments at Baseline and During Treatment

Procedures	Eligibility Assessments	During Treatment - 5 days ^a Inpatient						Post-treatment (PT) Inpatient
		Baseline/ Study Day 1 ^a	Study Day 2	Study Day 3	Study Day 4	Study Day 5 /day of last dose ^a	Study Day 6 if applicable ^b	
Written informed consent	X	X						
Subject demography	X	X						
Physical examination ^c		X	X	X	X	X	X	Daily
Influenza Test – locally performed (equipment provided by GSK)	X	X						
Medical/Prior Medication/Drug/Smoking History	X	X						
HIV and Liver Disease History ^d	X	X						
Influenza symptoms ^e	X	X						
HIV, Hep B and Hep C Test ^f	X	X						
Chronic underlying illness assessment	X	X						
Inclusion/Exclusion Criteria	X							
Safety/Efficacy Assessments								
Chest X-ray ^g		X						
ECG ^h	X	X				X	X	
Adverse events		X	X	X	X	X	X	Daily
Concomitant medications ⁱ		X	X	X	X	X	X	Daily
Complications of influenza/associated antibiotic use ^j		X	X	X	X	X	X	Daily
Vital signs (temperature, HR, BP, respiratory rate, oxygen saturation, ventilation status) ^k	X	X	X	X	X	X	X	3 x Daily
Flu PRO		X	X	X	X	X	X	Daily
Katz Activities of Daily Living ^l		X	X	X	X	X	X	Daily
Activity level ^m		X	X	X	X	X	X	Daily
Laboratory Assessments								

Procedures	Eligibility Assessments	During Treatment - 5 days ^a Inpatient						Post-treatment (PT) Inpatient
		Baseline/ Study Day 1 ^a	Study Day 2	Study Day 3	Study Day 4	Study Day 5 /day of last dose ^a	Study Day 6 if applicable ^b	
Chemistry including Liver Function Tests (Local+Central) ⁿ	X	X		X		X	X	Day 6,7,8
Serum creatinine (Local+Central) ^o	X	X	X	X	X	X	X	Day 6,7,8
Hematology (Local+Central) ^p	X	X		X		X	X	Day 6,7,8
Urine Output ^q		X	X	X	X	X	X	
Pregnancy test ^r	X	X						PT Day 3
Nasopharyngeal swab ^s		X		X		X	X	Day 8,12,16,20,24,28,32
Nasal Swab ^t	X	X						
BAL ^u		X		X		X	X	
Endotracheal aspirate ^v		X		X		X	X	Day 8,16,24,32, 45
Nasal SAM strips (biomarkers) ^w		X		X		X	X	Day 8,16,24,32, discharge or Day 45
Nasal washes ^x		X		X		X	X	Day 8,16,24,32, discharge or Day 45
Exploratory Biomarkers (Blood Sample)		X		X		X	X	Day 8,16,24,32, discharge or Day 45
PK sample (Dried Blood Spot) ^y		X		X		X	X	
Genetics Sample (Blood Sample) ^z		X						
Transcriptomics (Blood Sample) ^z		X		X		X	X	Day 8, 16, 24, 32, discharge or Day 45

Procedures	Eligibility Assessments	During Treatment - 5 days ^a Inpatient						Post-treatment (PT) Inpatient

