Table 4 Time and Events Table: Post-Treatment and Post-Discharge Assessments

Procedures	Post-Discharge Visits/TCs and Assessments Outpatient ^a					
	PT Day 3 (Visit)	Study Day 8 (TC)	Study Day 15 (TC)	Study Day 22 (TC)	Study Day 30 (TC)	Study Day 45 (Visit)
Safety/Efficacy Assessments						
Adverse events	X	X	X	X	X	X
Concomitant medications	X	X	X	X	X	X
Brief Physical Exam	X					X
Complications of influenza / associated antibiotic use ^b	X	X	X	X	X	X
Temperature	X	X	X	X	X	X
Other Vital signs (HR, BP, respiratory rate, oxygen saturation, ventilation status) ^c	X					X
Flu PRO ^d	Daily through Day 14	Daily through Day 14	X	X	X	X
Katz Activities of Daily Living ^e	X	X	X	X	X	X
Activity level ^f	Daily through Day 14	Daily through Day 14	X	X	X	X
Laboratory Assessments						
Clinical chemistry including LFTs ^g (Local+Central)	X					X
Serum Creatinine ^h (Local+Central)	X					X
Hematology ⁱ (Local+Central)	X					X
Pregnancy test ^j	X					
Nasopharyngeal swabs	X					
Exploratory Biomarkers (Blood Sample) ^k	X					X
Transcriptomics (blood sample) ^l	X					X
Nasal SAM strips (biomarkers) ^m	X					X
Nasal washes ⁿ	X					X
Hospital Readmission Status	X	X	X	X	X	X

a. Following discharge from hospital, outpatient clinic visit/TC schedule of assessments will be followed for those patients who are discharged before Day 45. For 5 days treatment, PT Day 3 will be the same as Day 8 and will be a clinic visit.

- b. Complications of influenza such as bacterial pneumonia, pneumothorax, pleural effusion, ARDS, myositis, encephalitis, myocarditis, and associated antibiotic use will be recorded on all assessment days.
- c. Vital signs and ventilation status will be assessed at clinic visits (PT Day 3 and Day 45).
- d. FLU PRO to be measured once daily through Study Day 14.
- e. Activities of Daily Living (Katz Scale) to be done at clinic visits and at TCs.
- f. Activity level assessed by reporting on a 3 point scale of bed rest (1), limited ambulation (2) or unrestricted (3) to be done daily through Study Day 14.
- g. Clinical chemistry including LFTs to be required once every other day until PT Day 3 (for LFTs, local testing for subject management until PT Day 3; central testing for all assessments, including at Day 45).
- h. Serum creatinine required once every day until PT Day 3 (local testing for subject management until PT Day 3; central testing for all assessments, including at Day 45).

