7.3.4. Virologic Measures and Biomarker Sampling

Samples for virologic measures and biomarker sampling will be collected locally as in the Time and Events Tables (Section 7.1). These samples will include nasal swabs, nasopharyngeal swabs, nasal samples (SAM strips and optional nasal washes), endotracheal aspirates (from intubated subjects), whole blood samples (ribonucleic acid [RNA] transcriptome analysis, deoxyribonucleic acid [DNA]), serum, and BAL samples from subjects where it is part of routine management. When multiple respiratory samples are to be taken at any visit, samples will be collected in the following order (Table 6).

Table 6 Sampling Order of Respiratory Samples for Virologic and Biomarker Assessments

Sequence of Collection	Sample Type	Study Day (inpatients)	Outpatient Assessments	Number and location of samples	Purpose
1	Nasal swab or nasopharyngeal swab	Day 1	N/A	Nare 1	Influenza diagnostic test
2	Nasal SAM strips	Day 1, 3, 5, 8, 16, 24, 32; also at discharge or Day 45	PT Day 3, Day 45	Both nares	Biomarker analysis
3	Nasopharyngeal swabs	Day 1, 3, 5, 8, 12, 16, 20, 24, 28, 32;	PT Day 3	Nare 2	Virology analysis
4	Nasal wash ^a	Day 1, 3, 5, 8, 16, 24, 32; also at discharge or Day 45	PT Day 3, Day 45	Both nares	Neutrophil counts/biomarker analyses
	Endotracheal samples ^b	Day 1, 3, 5, 8, 16, 24, 32, 45	N/A	ET aspirate	Neutrophil counts/biomarker analyses

a. Requested from subjects who are not intubated (optional procedure).

b. Required from subjects who are intubated.

- Nasal swabs will be collected at baseline to confirm influenza infection with a rapid influenza diagnostic test provided by GSK or other local test.
- Nasopharyngeal swabs will be collected for influenza Subtype RT-PCR, qRT-PCR, quantitative culture and may also be used for rapid influenza diagnosis. Nasopharyngeal samples will also be used for viral genotyping and phenotyping if needed and for multiplex PCR assay.
- Endotracheal (ET) aspirates will be collected from subjects who are intubated. The endotracheal samples will be used for biomarker evaluation and neutrophil counts (Section 7.6).
- Nasal SAM strips will be used to collect nasal samples and will be used for biomarker evaluation.

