9.4.3. Virology Analyses

Change from baseline in influenza viral load by qRT-PCR and by quantitative virus culture from nasopharyngeal swabs will be summarized and plotted by treatment and visit. Summary of proportion of subjects with no detectable influenza viral RNA by qRT-PCR and by quantitative virus culture from nasopharyngeal swabs.

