11.7. Appendix 7: Premature Withdrawals & Handling of Missing Data

11.7.1. Premature Withdrawals

Element	Reporting Detail
General	 Subject study completion (i.e. as specified in the protocol) was defined as a subject who completed the Day 45 assessment. Withdrawn subjects will not be replaced in the study. All available data from subjects who were withdrawn from the study will be listed and all available planned data will be included in summary tables and figures, unless otherwise specified.

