11.13.16. Virology Tables

No.	Populatio n	IDSL / TST ID / Example Shell	Title	Programming Notes
9.1.	IPP	VR T1	Summary of Change from Baseline in Influenza Viral Load by qRT-PCR (log 10 VP/mL) Overall	Includes baseline value Summarize by A and B combined
9.2.	IPP	VR T2	Summary of Change from Baseline in Influenza Viral Load by qVC (log10 TCID50/mL) for Subjects Culture Positive at Baseline –Nasopharyngeal	Includes baseline value
9.3.	ITTE	VR T7	Proportion of Subjects with Other Co-infected Viruses by Multiplex RT PCR.	
9.4.	IPP	VR T4	Summary of Resistance Associated Mutations Detected in the NA Gene by Subtype - Nasopharyngeal	
9.5.	IPP	VR T4	Summary of Resistance Associated Mutations Detected in the HA Gene by Subtype - Nasopharyngeal	

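### After post-treatment Day 3 only inpatients are swabbed, so late by-arm viral-load summaries are conditional on staying in hospital and can be biased

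*Protocol*

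**What the plan says.** - **Inpatients.** In protocol 7.1, Table 3, the post-treatment inpatient column lists nasopharyngeal swabs on "Day 8,12,16,20,24,28,32". Table 6 in 7.3.4 repeats this under its inpatient heading: "Day 1, 3, 5, 8, 12, 16, 20, 24, 28, 32".
- **Discharged subjects.** Table 4, note a: "Following discharge from hospital, outpatient clinic visit/TC schedule of assessments will be followed for those patients who are discharged before Day 45". In that schedule the nasopharyngeal swab is marked at PT Day 3 and nowhere else. Table 6 agrees. Note a adds: "For 5 days treatment, PT Day 3 will be the same as Day 8 and will be a clinic visit".
- **Early discharge.** Protocol 4.2: "If a subject is discharged from the hospital in less than 5 days, treatment with IV DNX will discontinue". PT Day 3 then falls before Day 8.
- **Analysis.** Under protocol 9.4.3, change from baseline in viral load, by qRT-PCR and by culture, "from nasopharyngeal swabs will be summarized and plotted by treatment and visit". The same section summarises the proportion with no detectable virus.
- **SAP.** Section 11.13.16 keeps Table 9.1, "Summary of Change from Baseline in Influenza Viral Load by qRT-PCR (log 10 VP/mL) Overall", and a matching culture table, 9.2. For withdrawn subjects, section 11.7.1 says "all available planned data will be included in summary tables and figures". Neither document has a virology rule for subjects no longer swabbed because they went home; the SAP's last-observation rule covers biomarker AUC only.

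**The concern.** From Day 12 a subject has a swab only if still in hospital. Discharge happens after randomisation, and protocol 7.3.1 counts it as a primary-endpoint response that DNX is meant to bring forward. A by-arm mean or percentage at Days 12 to 32 therefore compares two selected remnants rather than the randomised groups. If DNX changes length of stay, the remnants are selected differently, and a viral-load difference can appear, or be hidden, without any effect on virus.

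Protocol 4.6.1 names worsening of influenza virus-mediated disease as a potential risk of inhibiting neutrophils, so a reader may look to these displays for harm. Other samples in Table 3 (SAM strips, nasal washes, blood biomarkers) also have a collection at discharge or Day 45, and outpatients give them again at Day 45. The nasopharyngeal swab has neither.

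**Working it through.** **1. The plan's own recovery model.** Protocol 9.2.1 assumes exponential recovery with control medians m of 5.8 days (less severe) and 20.1 days (critically ill). Days gained = m − m/HR.

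- m = 5.8: 0.97 days at HR 1.2 and 1.93 at HR 1.5 (Table 8: 1 and 2).
- m = 20.1: 3.35 and 6.70 days (Table 8: 3.4 and 6.7).
- Hazard: ln2/5.8 × 7 = 0.837 per week (the plan gives 0.83 without a unit).

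Table 8 reproduces.

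**2. Share still without response, as a proxy for still in hospital.** SAP 11.6.1 makes treatment start Day 1 with no Day 0, so Day d is d − 1 elapsed days. S = exp(−(ln2/m) × HR × (d − 1)). With m = 5.8 and the planned 60/120/120 subjects (control, 15 mg, 50 mg):

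| Day | Control | HR 1.2 | HR 1.5 | Expected n |
|---|---|---|---|---|
| 8 | 43% | 37% | 29% | 26 / 44 / 34 |
| 12 | 27% | 21% | 14% | 16 / 25 / 17 |
| 16 | 17% | 12% | 7% | 10 / 14 / 8 |
| 20 | 10% | 7% | 3% | 6 / 8 / 4 |

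With m = 20.1 the Day 12 shares are 68%, 63% and 57%. Response can be met in hospital on vital signs, so the proxy understates the number still inpatient.

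**3. Possible artefact with no drug effect on virus.** Assumptions not in the documents: SD 1.5 log10; correlation r of 0.2 to 0.5 between viral load and slow recovery, the same in each arm. The mean standardised recovery rank among those remaining is k = φ(q)/S, where q is the normal quantile with upper tail S. Artefact (50 mg minus control) = 1.5 × r × (k50 − kcontrol).

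- Day 12: k = 1.593 and 1.228, so 1.5 × 0.365 × r = 0.55r, which is 0.11 to 0.27 log10. Standard error = 1.5 × √(1/16.1 + 1/16.7) = 0.52. Ratio 0.21 to 0.52.
- Day 16: k = 1.931 and 1.500, giving 0.13 to 0.32 log10. Standard error = 1.5 × √(1/10.0 + 1/8.2) = 0.71. Ratio 0.18 to 0.46.
- Critically ill median, Day 12: 0.05 to 0.13 log10.

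**4. Does the direction hold under other patterns?** A simulation with 2 million subjects per setting and no viral effect assumed a clearance slope with mean 0.30 and SD 0.10 log10/day, and a log discharge hazard falling by β per SD of slower clearance. Difference in mean change at Day 12, 50 mg minus control (positive means DNX looks slower):

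| How DNX speeds discharge | β = 0 | β = 0.5 | β = 1.0 |
|---|---|---|---|
| Multiplies every hazard by 1.5 | 0 | +0.21 | +0.19 |
| Adds a constant to every hazard | 0 | 0 | 0 |
| Acts only in slow clearers (hazard × 2.25) | −0.59 | −0.27 | +0.03 |

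In the first row with β of 0.5 or 1.0, about 9 percentage points fewer DNX subjects are undetectable at Day 12, taking a baseline of 5 log10 and a detection limit of 2.

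**5. Where selection starts.** By the same proxy, at 4 elapsed days 1 − exp(−(ln2/5.8) × HR × 4) gives 38% of control and 51% of HR 1.5 subjects already responded. Some subjects will be discharged before Day 5, so their last-dose and PT Day 3 swabs come early. Timing can differ by arm even before Day 8.

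**The case against.** The strongest objection is that little depends on these summaries. Virology is exploratory because DNX is not a direct-acting antiviral (protocol 4.4). The stopping and arm-dropping rules use time to clinical response. The SAP is descriptive for 10 subjects, disclaims definitive conclusions, and already plans individual viral-load plots (Figures 9.1 and 9.2) and a listing. The artefact is also below one standard error at the planned size. All of this stands and sets the weight of the point. It does not make the late by-arm comparison a randomised one.

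A reader might infer more: that faster recovery on DNX will make its arm appear to clear virus more slowly and so create a false safety signal. The documents do not support that. They say nothing about how viral load relates to discharge. The sign requires slow clearers to stay longer and DNX to raise all discharge hazards in proportion. The planning model in protocol 9.4.1.1 is proportional for time to clinical response, which makes that direction plausible. But it says nothing about discharge given viral load, and step 4 shows zero or reversed differences under other patterns.

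Nor should the SAP be read as repeating all of protocol 9.4.3. The titles of Tables 9.1 and 9.2 do not say by visit, and the shells are in a separate document. The SAP synopsis lists the undetectable percentage, but section 11.13.16 has no table for it.

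**Conclusion.** The point holds as a minor one. By-arm viral-load summaries after PT Day 3 are conditional on remaining in hospital and can be biased if DNX changes length of stay. The bias runs against DNX under a proportional effect with slow clearers staying longer, and is nil or reversed otherwise. Its size, about 0.1 to 0.3 log10 at Day 12, rests on the assumed SD and correlation, on time to clinical response standing in for discharge, and on the 5.8-day median applying to all subjects. With 10 subjects split 2/4/4 (assumed), the same proxy leaves about 0.5, 0.8 and 0.6 subjects at Day 12 (control, 15 mg, 50 mg), so late arm means would carry almost no information.

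**What to change.** In protocol 9.4.3, and in SAP Tables 9.1 and 9.2 if their shells are by visit:

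- Limit between-arm means and percentages to swabs scheduled regardless of discharge, from baseline to PT Day 3 (the Day 8 swab in inpatients after a full course).
- Analyse them at actual study day, because early discharge moves the last-dose and PT Day 3 swabs before Day 8. At the planned size a mixed model using all swabs to PT Day 3 would do this; it still relies on an assumption about the days that early-discharged subjects miss. SAP 11.5.3 defaults to planned time, so the exception must be written in. With 10 subjects no model is needed.
- Show n per arm and visit.
- Present Days 12 to 32 only as individual inpatient profiles or listings, labelled as conditional on remaining in hospital.

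The cost is analysis and table wording, plus the loss of late by-arm means. No data are lost. If late comparisons matter in a future trial, swabbing on fixed days whether or not the subject is discharged removes this selection by design, at the price of extra outpatient visits.

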7.2. Critical Baseline Assessments

- Demographic parameters to be collected include: year of birth, sex, race and ethnicity. Date and primary reason of hospitalization (influenza or not influenza related) will be recorded and if applicable, the date of intubation.
- Nasal swabs or nasopharyngeal sample will be taken for confirming an influenza infection. A rapid diagnostic influenza test will be provided by GSK or other local, validated laboratory test for influenza can be used.
- Vital signs to include temperature, heart rate, systolic and diastolic blood pressure, respiration rate, oxygen saturation. Oxygen delivery and ventilation status to be recorded approximately within approximately 1 hour prior to administration of the first dose of study medication;
- Influenza symptoms will be assessed at baseline prior to administration of study treatments. The presence of the following symptoms will be recorded: nasal symptoms (rhinorrhea, congestion), feverishness, cough, myalgias, fatigue, diarrhea, dyspnea, headache, sore throat, nausea and vomiting. The date of first onset of influenza like symptom(s) will also be recorded. The investigator or designee will assess and record influenza symptoms based on interview with the subject. In situations when subjects may not be able to communicate their symptoms, for example in subjects ventilated and/or sedated, the investigator or designee will record those signs/symptoms as ‘unable to assess’;
- Cardiovascular medical history/risk factors (as detailed in the CRF) will be assessed at baseline.
- Medical/medication/family history will be assessed as related to the inclusion/exclusion criteria listed in Section 5.
- Chronic underlying illness (including but not limited to asthma, COPD, diabetes, hypertension, Congestive Heart Failure) will be recorded.
- Pre-morbid functional status (defined as the best functional status in the 4 weeks prior to enrolment) and status at Baseline as measured by the Katz ADL scale and activity level (bed rest, limited ambulation or unrestricted) will be recorded in the eCRF. For subjects unable to communicate their pre-morbid functional status, this information should be requested from another close member of the household, close family member, or the subject’s regular physician (if the subject has been under the care of a single physician for 3 months or longer).
- Laboratory evaluations:
 - Samples for clinical chemistry and hematology will be collected for analysis at a central laboratory (Table 7).
 - Samples for serum creatinine concentration, CBC with differential and liver function tests (LFTs) will also be obtained locally. The calculated creatinine clearance value will be recorded in addition to the serum creatinine concentration. Absolute neutrophil counts (ANC) and LFTs will be recorded.

- Nasopharyngeal swab to be collected prior to dosing for influenza subtype RT-PCR, qRT-PCR, quantitative culture and viral phenotype and genotype analysis and multiplex PCR.
- An endotracheal aspirate is requested only if the subject is intubated and a BAL sample is requested only if the procedure/sampling is being carried out for the routine management of the patient.
- Nasal Synthetic Absorption Matrix (SAM) strips will be used to collect samples from all subjects.
- An optional nasal wash procedure will be used for collecting samples and is requested from subjects who are not intubated;
- An ultrasensitive urine pregnancy test will be performed on women of childbearing potential;
- ECG: One baseline 12-lead ECG is required within approximately 24 hours prior to dosing. Any ECG that has been performed for clinical care can be utilized. A monitoring strip can also be utilized if a 12-lead ECG cannot be performed.
- Chest X-ray: Chest X-ray results (abnormal findings and normal findings) should be taken within 48 hours before the first dose of study medication and are to be recorded in the eCRF.

Procedures conducted as part of the subject's routine clinical management and obtained prior to signing of informed consent may be utilized for Baseline purposes provided the procedure meets the protocol-defined criteria and has been performed within the timeframe defined in the Time and Events Schedule.

Patient Reported Outcomes questionnaires should be completed by subjects before any other assessment at a clinic visit, in the order specified.

Limited data will be collected on subjects who withdraw after providing informed consent but before initiation of treatment in the eCRF.

7.3. Efficacy

Clinical, virological and health outcomes assessments will be conducted as described in the Time and Events Tables [Table 3](#), [Table 4](#), to evaluate endpoint detailed in Section [7.3.3](#), Section [7.3.4](#), Section [7.3.5](#).

7.3.1. Primary Endpoint

The primary endpoint is time to clinical response (TTCR) ([Table 5](#)).

Clinical response is defined as resolution of at least 4 of the 5 signs described below within the respective resolution criteria, maintained for at least 24 hours, or hospital discharge, whichever comes first.

Table 5 Criteria for Time to Clinical Response

Sign of clinical response	Response criteria
Hospital discharge	Subjects who are discharged from hospital will be considered to have met the clinical response endpoint at the time of hospital discharge and are not required to have documented resolution of at least 4 response criteria (i.e. achieved success at the time of discharge if not observed prior to it).
OR	
Temperature ¹	≤36.6°C (≤97.9°F) – axilla, or ≤37.2°C (≤99°F) – oral, or ≤37.7°C (≤99.9°F) – rectal/core ⁵ , tympanic
AND	
Oxygen saturation ^{2,3}	≥95% (without supplemental oxygen)
AND 2 out of the following 3 criteria:	
Respiratory status	
 Return to pre-morbid oxygen requirement (subjects with chronic oxygen use), OR Need for supplemental oxygen (administered by any modality – ventilator, non-invasive ventilation, facemask, facemask, nasal canula, etc) to no need for supplemental oxygen, OR Respiratory rate ≤24/min (without supplemental oxygen)
Heart rate	≤100/min
Systolic blood pressure ⁴	≥90 mmHg

- Without the use of antipyretics within 8 hours
- A subject with a history of chronic hypoxia (without supplemental oxygen) will satisfy normalization criteria for oxygen saturation if the value (without supplemental oxygen) is ≤2% from subject's historical oxygen saturation baseline as recorded within 12 months prior to enrolment as documented in the subject's medical records.
- This requirement will be waived for subjects with a history of chronic supplemental oxygen requirement who have a baseline oxygen saturation <95% with supplemental oxygen, within 12 months prior to enrolment as documented in the subject's medical records.
- Without inotropic support administered within 2 hours.
- Core temperatures include measurements via a temporal artery thermometer, indwelling catheters and Swan Ganz catheters.

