3. OBJECTIVES AND ENDPOINTS

Objectives	Endpoints
Primary	

 To assess the efficacy of treatment with IV DNX twice daily given with oral oseltamivir compared to oral oseltamivir twice daily on time to clinical response (TTCR) 	
 Time to Clinical Response (composite) 
 Hospital discharge OR 
 Normalization of: 
 -- Temperature; and --Oxygen saturation; and --Respiratory status/Heart Rate/SBP (normalization of 2 out of these 3 parameters)
Secondary	

 To assess the efficacy of treatment with IV DNX twice daily given with oral oseltamivir compared to oral oseltamivir twice daily on time to respiratory response (TTRR) 	
 Time to Respiratory Response defined as meeting at least one criterion below 
 Return to pre-morbid oxygen requirement (subjects with chronic oxygen use), OR Return to no requirement of supplemental oxygen, OR Respiratory rate ≤ 24/min (without supplemental oxygen)

 To evaluate clinical measures of influenza illness following treatment with IV DNX twice daily given with oral oseltamivir compared to oral oseltamivir twice daily 	
 Time to absence of fever Time to improved oxygen saturation Time to improved heart rate Time to improved SBP Proportion of subjects with clinical response over time Proportion of subjects with improved respiratory status over time Time to improvement of ventilation status: modality, frequencies and durations of invasive and non-invasive ventilator support, duration of oxygen supplementation. Length of stay in the ICU Frequency of ICU admission and

Objectives	Endpoints
	readmission 
 • Length of stay in the hospital • Rates of development of septic shock • Frequency of antibiotic use • Proportion of subjects with improvement in Ordinal scale of clinical efficacy over time : 
 • Death • Mechanical vent • In the ICU • Non-ICU hospitalization • Hospital discharge

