5.1. Inclusion Criteria

A subject will be eligible for inclusion in this study only if all of the following criteria apply:

AGE
1. Adults 18 years (as per local laws) of age and older at the time of signing the informed consent.
TYPE OF SUBJECT AND DIAGNOSIS INCLUDING DISEASE SEVERITY

2. Presence of fever ($\geq 38.0^{\circ}\text{C}$ [$\geq 100.4^{\circ}\text{F}$] by any route) at Baseline (enrollment) or history of fever/feverishness during the 48 hours prior.
 
3. O_2 saturation $< 95\%$ on room air by trans-cutaneous method OR need for any supplemental oxygenation (non-invasive ventilation, facemask, facetent, nasal canula, etc) or ventilator support (mechanical ventilation, bi-level positive airway pressure [BIPAP], continuous positive airway pressure [CPAP]) or increase in oxygen supplementation requirement of ≥ 2 liters for subjects with chronic oxygen dependency. For those subjects with a history of chronic hypoxia (without supplemental oxygen), an oxygen saturation of at least 3% below the subject's historical baseline oxygen saturation.
 
AND AT LEAST 2 out of the following 3:
 
 • Respiratory rate > 24 breaths per minute. For those subjects who require ventilator support or oxygen supplementation, this requirement is waived. • Heart rate > 100 bpm • Systolic bp < 90 mm Hg. 
4. Severity of symptoms at enrollment:
 
 • Less severe hospitalized subjects are those who (but not limited to): 
 • are hemodynamically stable; • may require oxygenation with facemask, facetent, nasal canula, etc; • may or may not have radiological signs of lower respiratory tract disease; or • have exacerbation of underlying chronic disease, including asthma, chronic

obstructive pulmonary disease (COPD), or other cardiovascular conditions not leading to hemodynamic compromise.

- Critically ill hospitalized subjects are those who (but not limited to):
 - require CPAP, BIPAP, mechanical ventilation;
 - have hemodynamic instability (with or without pressor support); or
 - have central nervous system involvement (eg encephalopathy, encephalitis).
- 5. Presence of influenza that in the Investigator's judgment requires hospitalization for treatment and supportive care

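### For some subjects on chronic oxygen, the saturation rule in the primary endpoint either leaves discharge as the only route to response or allows a response on ventilatory support

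*Protocol*

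**What the plan says.** Chronic-oxygen subjects are eligible by name. Inclusion criterion 3 (protocol 5.1) admits an "increase in oxygen supplementation requirement of ≥ 2 liters for subjects with chronic oxygen dependency", and the same criterion admits ventilated subjects.

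Protocol 7.3.1, Table 5, builds clinical response from five signs, held for 24 hours, with discharge as the alternative. Temperature is required. Saturation is required, at "≥95% (without supplemental oxygen". Then comes "AND 2 out of the following 3 criteria": respiratory status, heart rate and systolic pressure. The objectives table (protocol section 3) has the same structure, ending in "normalization of 2 out of these 3 parameters".

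Two notes adapt the saturation row:
- Note 2: "A subject with a history of chronic hypoxia (without supplemental oxygen) will satisfy normalization criteria for oxygen saturation if the value" lies within 2% of the subject's own historical figure. It is limited to subjects not on chronic oxygen.
- Note 3 reads: "This requirement will be waived for subjects with a history of chronic supplemental oxygen requirement who have a baseline oxygen saturation <95% with supplemental oxygen", with that value documented in the 12 months before enrolment. Nothing replaces the waived sign.

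The respiratory-status row does recognise this group: "Return to pre-morbid oxygen requirement (subjects with chronic oxygen use" counts. But it is only one of the two-of-three options.

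The sentence introducing Table 5 states a different rule, "resolution of at least 4 of the 5 signs described below", and the discharge row also refers to four criteria. SAP 7.1.2 repeats the table and note 3, leaves out the four-of-five sentence, and adds no condition on ventilation or oxygen support.

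**The concern.** TTCR is meant to mark recovery from a respiratory illness. For chronic-oxygen subjects, the mandatory saturation row and the optional respiratory-status row do not agree on what recovery is. A subject back at the usual home flow counts as recovered in one row and, if not waived, as unrecovered in the other. A waived subject has no mandatory respiratory condition at all.

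The ordering is also inverted. The better-oxygenated chronic user faces the harder endpoint and the worse-oxygenated user the easier one. For these subjects the event time can reflect discharge practice, or the settling of heart rate and temperature, instead of oxygenation. Protocol 4.4 expects the drug to act mainly in the lung, so this blurs the primary endpoint in the dimension of most interest.

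**Working it through.** The plan states no figure to reproduce here. The check is of the logic.

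**Notation.** T temperature, S saturation sign met, W waiver applies, R respiratory status, H heart rate, B systolic pressure; each is 0 or 1.

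- Table 5 and SAP 7.1.2: response if T = 1, and (S = 1 or W = 1), and R + H + B ≥ 2.
- Four-of-five sentence: response if T + S + R + H + B ≥ 4. It does not say whether a waived S counts as 1.

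**Case A.** Documented 96% on 2 L, so no waiver. Now back at 2 L with temperature, heart rate and pressure normal, but below 95% off oxygen. T=1, S=0, W=0, R=1, H=1, B=1.
- Table: the saturation term fails, so no response. With S=0 and W=0, none of the 16 combinations of the other four signs responds. Discharge is the only route.
- Sentence alone: 1+0+1+1+1 = 4, so response.

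A chronic-oxygen subject with no saturation record within 12 months is in the same position.

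**Case B.** Documented 93% on 2 L, so waived. Now on BIPAP or a ventilator, above the usual support. T=1, S=0, W=1, R=0, H=1, B=1.
- Table: temperature met, saturation waived, R+H+B = 0+1+1 = 2, so response after 24 hours.
- Sentence alone: 1+1+0+1+1 = 4 (response) if the waived sign is counted; 1+0+0+1+1 = 3 (no response) if it is not.

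Notes 1 and 4 still apply: no antipyretics within 8 hours and no inotropic support within 2 hours. They make Case B harder to reach but do not test breathing.

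**Case C.** The same ventilated state without the waiver (S=0, W=0, R=0). None of the 8 combinations of T, H and B responds. With the waiver, 1 of 8 does (all three normal). So for a ventilated subject who does not meet the saturation sign, that row is the only bar to a response, and note 3 removes it.

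**Where the two protocol rules differ.** With no waiver, over all 2^5 = 32 combinations they disagree in two: only saturation unmet (Case A), and only temperature unmet.

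**Size.** The documents give no prevalence of chronic oxygen use. Assuming 5-15%:
- 0.05 × 300 = 15 and 0.15 × 300 = 45 of the planned subjects;
- 0.05 × 60 = 3 and 0.15 × 60 = 9 of the planned controls.

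These are subjects to whom the rule applies. Case A also needs inability to hold 95% off oxygen, and recovery before discharge. Case B also needs normal temperature, heart rate and pressure for 24 hours while support is still raised. A waived subject already back at the usual oxygen when the other signs settle is scored as intended. The split between these groups is not in the documents.

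**The case against.** The best reply on the protocol is the four-of-five sentence. Read alone it resolves Case A, and it blocks Case B if a waived sign is not counted. But it contradicts the AND structure of the table and of the objectives, it is silent on waived signs, and the SAP, which governs the derivation, does not carry it. It shows a second defect to reconcile and does not remove the first.

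Several other replies stand.
- Discharge is a designed component of TTCR, so Case A delays the event and does not lose it.
- Some chronic users can hold 95% off oxygen and are unaffected.
- Time to respiratory response (protocol 7.3.2, SAP 11.6.4) credits return to the usual oxygen directly.
- The rule is the same in every arm of a blinded trial. A reader might infer bias in the treatment comparison; the documents give no basis for that.

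The strongest limit is the study's actual course. It stopped after 10 subjects, with descriptive analysis only (SAP 2.1). Protocol 4.1.2 holds back critically ill subjects, which includes those on CPAP, BIPAP or a ventilator, until about 30 less severe subjects have been reviewed. By protocol, none of the 10 should have entered ventilated, so Case B could arise only through later deterioration. The SAP also lists TTCR, ventilation and oxygen data by subject (Listings 31, 34 and 35), so a mis-scored subject could be seen.

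**Conclusion.** The point holds as a defect in the endpoint definition. Under Table 5 and SAP 7.1.2, some chronic-oxygen subjects who have returned to their usual oxygen can respond only by discharge, and others can be recorded as responders while still on added ventilatory support. This follows from the wording and does not depend on prevalence.

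Its size is not known. A reader might take 15-45 of 300 as the number scored wrongly. That is not supported: the range rests on an assumed 5-15% prevalence and is an upper bound on those exposed to the rule. Nor can Case B be set against the 20.1-day median for critically ill subjects (protocol Table 8) as if it were an effect; one hypothetical subject says nothing about the hazard ratio, and no effect on the hazard ratio or power can be computed.

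For the analysis now planned, the consequence is confined to individual TTCR values and Kaplan-Meier medians. Ten subjects at 2:2:1 is about 4, 4 and 2 per arm (10 × 2/5, 10 × 2/5, 10 × 1/5), so one misdated event could move a median. A reader might also conclude that the analysis cannot proceed until this is settled; with descriptive summaries and full listings, that goes too far. It is worth correcting, at moderate priority.

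**What to change.** In protocol Table 5 and SAP 7.1.2, replace note 3 with one rule for every subject with a chronic oxygen requirement: the saturation sign is met when the subject is back at the pre-illness oxygen requirement and saturation at that flow is at least 95%, or within 2% of the historical on-oxygen value. This parallels note 2, covers both groups, agrees with the respiratory-status row and keeps an oxygenation condition for everyone. A subject with no historical record would be scored on the 95% limb; the note should say so.

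Then reconcile the four-of-five wording, in the sentence introducing Table 5 and in its discharge row, with the AND structure, so that the protocol carries one rule and it matches the SAP. Any change to the SAP should be made before unblinding.

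The cost is wording in both documents and a small change to the derivation. It alters scoring only, not care. Oxygen modality and quantity are already recorded (protocol 7.3.3), and saturation history is planned for SAP Listing 35. The one downside is that this subgroup's definition would differ slightly from that in the earlier intravenous zanamivir study behind the control-arm prior. That prior is not used in the descriptive analysis, so the point would matter only if the Bayesian design were taken up again.
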